## 2) Objectives

The objective of this pilot study is to collect preliminary data using total body scans on a new, first of its kind, FDA 510k-cleared positron emission tomography/computed tomography (PET/CT) scanner, called EXPLORER. Built by United Imaging Healthcare (UIH) in collaboration with investigators at UC Davis, EXPLORER has the potential to significantly alter the practice of PET/CT. This initial pilot study will have the following broad objectives:

Objective 1: To obtain preliminary data on (a) delayed, (b) low-dose and (c) total body dynamic acquisitions on the EXPLORER PET/CT scanner.

Objective 2: (d) To obtain preliminary data regarding possible impacts on F fluorodeoxyglucose (FDG) PET image quantification related to use of intravenous iodinated contrast agent with the EXPLORER PET/CT scanner.

## 3) Background

The 194 cm long EXPLORER total-body PET scanner is the world's first device to offer the ability to tomographically image all parts of the body simultaneously. It has the potential for a signal sensitivity gain of ~40-fold compared to existing commercially available devices for total-body applications. Spatial resolution is also comparable to or better than all other commercially available clinical devices available today. Answering the basic questions that this new equipment poses constitutes an important advancement for both clinical and academic settings.

(A) The distribution of radiotracer activity depends on post-injection imaging time for both anatomical structure and pathologic processes. Different anatomic structures and different pathologic abnormalities are characterized by different time-activity curves. However, delayed imaging results in lower signal due to radioactive decay and physiological washout, which has so far limited the evaluation of late time-to-activity curves due to the low sensitivity of conventional scanners. The increased sensitivity of EXPLORER has the potential to overcome this limitation and allow for high-quality delayed scans. We seek to obtain preliminary data regarding the time-course of the most commonly-used PET radiotracer F fluorodeoxyglucose (FDG) concentration in tissues over a twelve-hour period. In addition, for precise characterization of FDG clearance through the urinary system we will assess radiotracer activity in urine collected from

PROTOCOL TITLE: [1341792] EXPLORER PET/CT: A Pilot Evaluation in Healthy Volunteers

Version 9 01/27/2021

subjects. Assessment of excreted FDG will increase the precision of estimated SUV values. For analysis of small structures in the brain, we will use MRI to guide region of interest placement - this has been standard practice in multiple studies for the last 25 years.

(B) EXPLORER PET/CT allows for the possibility of very low-dose imaging. This is clinically important for pediatric patients who may have multiple scans and are more impacted by the stochastic effects of radiation than the adult population. It is also important for research, where the subjects receive no benefit from the radiation exposure associated with the scan. However, we do not have information on the statistical quality of low-dose scans with EXPLORER and this information is essential for power calculations for future studies.

(C) EXPLORER whole body PET/CT is the only scanner in the world capable of acquiring total body dynamic images. Acquisition of dynamic images will allow new applications such as organ perfusion imaging. Available PET/CT scanners can obtain perfusion images only on a portion of the body as large as their axial field of view, generally anywhere between 15-30 cm. EXPLORER can cover the total body and provide useful perfusion data in addition to early FDG biodistribution data and other functional parameters. We seek to obtain preliminary data regarding perfusion and early biodistribution images; this will be vitally important for the design of future studies.

(D) Intravenous iodinated contrast is commonly used in routine CT to increase the visualization of both anatomic and pathologic processes. Physically, the presence of iodine atoms increases the attenuation coefficient for CT radiation of the tissues in which it distributes by increasing the cross-section for photoelectric interactions. Applying attenuation correction algorithms for PET using contrast CT images has the potential to overcorrect the PET emission signal (which is much less susceptible to photoelectric interactions), introducing possibly significant errors in the final uptake quantification. While several studies have demonstrated that there is no statistically significant increase in uptake values upon injection of iodinated contrast when normal anatomic structures are assessed, at the present time, there is no study validating the use of contrast enhanced CT for attenuation correction purposes on the EXPLORER PET/CT scanner. We seek to obtain preliminary data to understand the impact of intravenous iodinated contrast agent on quantification of PET images.

#### **4) Inclusion and Exclusion Criteria**

Inclusion criteria:

- Men and women, 18 years of age or older
- Willing and able to fast for at least 6 hours before and for the duration of the scan
- Willing to provide urine sample throughout scan visit
- Willing and able to lay motionless in a supine position for 60 and 20 minutes at separate timepoints.
- Willing and able to give informed consent, personal contact information (phone number, email and postal address), insurance information, and primary care physician contact.

Exclusion criteria:

- No Primary Care Physician
- No health insurance
- Body weight more than 240 kg (529 pounds)
- Allergy to iodine contrast (only for subjects enrolled in Arm 3)
- Creatinine levels > 1.5 mg/dL or estimated glomerular filtration rate (eGFR) < 60 ml/minute (only for subjects enrolled in Arm 3)
- Recent (within 90 days) contrast enhanced CT (only for subjects enrolled in Arm 3)
- Any known concomitant acute infection (including upper respiratory infection, genitourinary infections, etc.)
- History of metastatic or newly (last 5 years) diagnosed locally invasive cancer.
- Chemotherapy in the last 5 years
- Radiation therapy in the last 3 years
- Major surgery within the last 6 months.
- Pregnancy or breast-feeding
- Diabetes
- Fasting blood glucose level > 160 mg/dL before administration of FDG
- Prisoners
- The standard MRI contraindications will be applied, according to UC Davis Department of Radiology Magnetic Resonance Safety Policy ID 1727, which may include:
  - Having a pacemaker or other implanted electronic device,
  - Metal foreign bodies, aneurysm clips, heart valve prosthesis, vascular stents, cochlear implants, embolization coils, gunshot wounds with retained bullet fragments, certain types of penile implants, and certain types of intrauterine devices (IUDs).
  - Claustrophobia

## 5) Study Timelines

- Subject participation: Each subject will participate in a single arm of this three-arm study (please see below), for up to approximately 13 hours during a single study visit (Study Arm 1), 4 hours for Study Arm 2 and 2 hours for Study Arm 3.
- Enrollment duration: We anticipate completing enrollment within 8 months.
- Primary data analysis duration: We anticipate completing primary data analysis within 12 months.

## 6) Study Endpoints: all study endpoints are exploratory

### *A. To collect preliminary data regarding FDG biodistribution as a function of time*

Population: Study Arm 1

Explanation: Changes are measured quantitatively from time-activity curves (TACs) generated for different organs using regions of interest (ROIs).

### *B. To obtain preliminary data regarding low dose EXPLORER protocols*

Population: Study Arm 2

Explanation: Regions of interest (ROI) will be placed in several organs; pixel intensity and coefficient of variation within ROI will be recorded.

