*Arm 2 (N=15; low FDG dose imaging):*

For Study Arm 2, 0.5 +/- 0.1 mCi of F-FDG (1/20th of the standard dose) will be hand injected through the IV and a 60-minute dynamic scan will begin on EXPLORER. The dynamic scan will be preceded by an ultra-low-dose CT scan (estimated dose of 1.298 mSv) for attenuation correction. The standard 20-minute EXPLORER scan obtained at 90 minutes will be obtained after a low dose CT (estimated dose of 7.44 mSv) for attenuation and co-localization. The standard 20-

PROTOCOL TITLE: [1341792] EXPLORER PET/CT: A Pilot Evaluation in Healthy Volunteers  
Version 9 01/27/2021  
minute EXPLORER scan obtained at 3 hours will be preceded by an ultra-low-dose CT scan (estimated dose of 1.298 mSv) for attenuation correction only.

*Arm 3 (N=15; comparison PET images reconstructed using CT-based attenuation correction acquired with and without iodinated contrast enhancement):*

For Study Arm 3, 10 +/- 2 mCi of F-FDG will be hand injected through the IV and a 60-minute dynamic scan will begin on EXPLORER. Prior to the dynamic scan, an ultra-low-dose CT scan (estimated dose of 1.298 mSv) will be acquired for attenuation correction purposes only. At 90 mins, a low dose non contrast enhancement CT (estimated dose of 7.44 mSv) will be acquired vertex to toes. Iodinated contrast (150 cc of iodine Omnipaque 350) will then be intravenously injected (through the same IV placed to inject FDG) at 3 ml/sec while the patient remains still on the scanner and a second low-dose CT will be acquired. Finally, a 20-minute PET acquisition will be performed. The IV line will be removed after completion of the study.

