Image reconstruction and analysis: Data from EXPLORER (all the three study arms) will be acquired in listmode. Data will be reconstructed using manufacturer's recommendations. Image quality, quantitative comparisons and preliminary biodistribution data collection will be performed by means of regions of interest (ROIs) drawn in different organs and tissue types where pixel intensity and coefficient of variation within ROIs will be computed and recorded.

Statistical considerations:

Since this is a pilot exploratory study on a first-of-its kind scanner, no formal power analysis is presented.

Exploratory data analysis will be conducted to examine the distribution of the data. Graphical methods including box-plots and histograms will be employed to examine the distributions of the measures. For all continuous variables, descriptive statistics, including means, ranges, and standard deviations will be computed. Ninety-five percent confidence intervals will be computed for means and proportions to obtain interval estimates of all measurements across image. For categorical data, frequency, proportions, and percentages will be calculated.

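### Endpoint B's summary of low-dose image noise pools over body size, although Arm 2 gives one fixed activity to adults of any weight up to 240 kg

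*Combined protocol and SAP*

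**What the plan says.** - **Activity and size.** Section 7 gives all Arm 2 subjects (N=15) a fixed 0.5 mCi with a tolerance of 0.1 mCi either way, not scaled to weight. Section 4 admits adults only. Its one size criterion is a ceiling of 240 kg, with no lower weight limit and no BMI limit. Under section 7, participants choose their own arm while places remain, so nothing controls the size mix.
- **Measure.** Section 6, Endpoint B, uses ROIs in several organs, where "pixel intensity and coefficient of variation within ROI will be recorded". Arm 2 has static scans at 90 minutes and 3 hours.
- **Analysis.** Section 7, Statistical considerations: "For all continuous variables, descriptive statistics, including means, ranges, and standard deviations will be computed". Confidence intervals at 95% are added for means and proportions. Weight, body size and activity per kg are not named as covariate, stratum or normaliser.
- **Purpose.** Section 3 (B) says the statistical quality of low-dose scans on this scanner is unknown and that "this information is essential for power calculations for future studies". It motivates low-dose imaging partly by children: "This is clinically important for pediatric patients who may have multiple scans".
- **Status.** The heading of section 6 states that "all study endpoints are exploratory".

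**The concern.** Noise in a PET image depends on the counts collected. When everyone receives the same activity, a heavier subject has less activity per kg of tissue, and more of the emitted signal is attenuated on its way out. Both raise the CoV. A mean and SD taken over subjects of different build, with no size term, mix this predictable effect with the remaining between-subject variation.

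Expressing pixel values as SUV would not help. CoV is a ratio, so rescaling all of a subject's pixels by weight and injected activity leaves it unchanged.

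At stake is the use that section 3 (B) gives for these data. A later study may recruit people of a different build, or scale activity to weight. From the planned summary, its designers could not tell what CoV to expect or how much of the SD would remain.

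**Working it through.** **Figures the plan states.** 0.5/10 mCi = 1/20, as section 7 says. 240 kg x 2.20462 = 529 lb, as section 4 says. N=15 is given without inputs (section 7 presents no power analysis), so there is no calculation to reproduce.

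**Activity per kg.** 0.5 mCi = 18.5 MBq. Dividing by weight gives 0.37 MBq/kg at 50 kg, 0.26 at 70 kg and 0.185 at 100 kg, a two-fold range from 50 to 100 kg.

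**Effect on CoV.** The documents give no noise model, so two assumed cases bracket it, with the same ROI, scan time and reconstruction throughout:

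- *Case 1, activity per kg only:* CoV proportional to 1/sqrt(activity per kg), so the ratio is sqrt(W2/W1).
- *Case 2, with attenuation:* the subject is a water cylinder of diameter d = 2 x sqrt(1000W/(pi x H)), with 0.096 per cm at 511 keV. The ratio is sqrt[(W2/W1) x exp(0.096 x (d2 - d1))]. Heights are assumed.

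| Comparison (kg/cm) | d1, d2 (cm) | Case 1 | Case 2 |
|---|---|---|---|
| 60/168 v 100/175 | 21.3, 27.0 | sqrt(1.667) = 1.29 | sqrt(1.667 x 1.72) = 1.69 |
| 50/165 v 120/175 | 19.6, 29.6 | sqrt(2.4) = 1.55 | sqrt(2.4 x 2.59) = 2.49 |

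For scale, the full dose tolerance gives sqrt(0.6/0.4) = 1.22, and the 20-fold activity reduction itself gives sqrt(20) = 4.47.

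**Spread that weight adds.** Assume lognormal weight with mean 80 kg and SD 10 to 20 kg. Weight alone then gives a relative SD of CoV of about 6 to 12% (case 1) or 14 to 28% (case 2).

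**What this could do to a later power calculation.** In case 1, the log-CoV SD due to weight is half the log-weight SD. The log-weight SD is sqrt(ln(1 + (SD/80)^2)) = 0.125 to 0.246, so the variance due to weight is 0.0039 to 0.0152. Assume a residual log-CoV SD of 0.10 to 0.15 (variance 0.0100 to 0.0225). For a design that removed the size effect, the unadjusted variance would be too large by a factor between 1 + 0.0039/0.0225 = 1.17 and 1 + 0.0152/0.0100 = 2.52.

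**Can 15 subjects support a fit?** For log CoV on log weight, the 95% half-width of the slope is t(13) x residual SD / (log-weight SD x sqrt(14)).

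- Best case: 2.16 x 0.10/(0.246 x 3.74) = 0.23.
- Worst case: 2.16 x 0.15/(0.125 x 3.74) = 0.70 (0.6956 unrounded).

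The expected size of the slope is 0.5 in case 1. In case 2 it is about 1.0, since ln(1.69)/ln(1.667) = 1.03 and ln(2.49)/ln(2.4) = 1.04.

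**Precision of the planned summary.** At n=15 the 95% interval for a mean is +/-0.55 SD. The interval for the SD runs from 0.73 to 1.58 times its estimate.

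**The case against.** The strongest reply is that this is a pilot with exploratory endpoints. Its aim is first data on low-dose scanning, and a CoV per organ with range, SD and interval provides that. Nothing is lost: section 7 keeps listmode data, section 9 banks images and dose reports indefinitely, every subject has CT, and the weight criterion together with the mention of SUV in section 3 implies that weight is known. All of this stands. It makes the point an omission from the analysis plan, not a failed endpoint. It does not explain why a known and measurable driver of the outcome should be left out of the summary.

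The documents do not support several stronger readings that a reader might infer:

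- *All CoV values go into one distribution.* Endpoint B covers several organs and Arm 2 has two static time points. Nothing says they are pooled. The fair reading is one unadjusted summary per organ and time point, pooled over size.
- *The results cannot be carried to later studies.* That is too strong even for the planned summary, and wrong for the data. A later adult study with the same fixed activity and similar recruitment, analysed without size adjustment, would find the unadjusted SD the right planning input.
- *The spread will be mostly body size.* The documents give no CoV variance to partition, and the share depends on who enrols. The 240 kg limit is a ceiling, not an expected range.
- *Arm 2 promises pediatric estimates.* Section 3 offers children as a motivation. Endpoint B makes no such promise and enrolment is restricted to adults.

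It is also fair to object that the larger ratios rest on the steep attenuation model, which is why both cases are shown. The slope may also be too imprecise to distinguish from zero: at the wide end, 0.5 +/- 0.70 includes it.

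**Conclusion.** The point holds as a gap in the analysis plan that is cheap to close. At fixed activity, ordinary differences in adult weight could change CoV by about 1.3- to 1.7-fold (60 v 100 kg) or 1.55- to 2.5-fold (50 v 120 kg). Even the lower figures exceed the 1.22-fold effect of the whole dose tolerance. The planned mean and SD are specific to the size mix of the volunteers. They are a poor input where the size mix differs or activity is scaled to weight.

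This rests on the inverse-square-root noise model, on the assumed cylinder and heights for the upper figures, and on assumed weight and residual SDs for the variance and slope calculations. None of these comes from the documents. The direction of the effect does not depend on the exact values; its size does.

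**What to change.** In Endpoint B (section 6) and the statistical considerations (section 7):

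1. State that weight, height and net injected activity are recorded for each subject.
2. For each organ and static time point, plot CoV against activity per kg or body size (weight, or effective diameter from the CT already acquired).
3. Keep the planned summary and report beside it a simple fit, for example log CoV on log activity per kg, with the interval for the slope and the residual SD.
4. State the size range actually studied.
5. Label any extrapolation below adult size as model-based.

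The cost is a few lines of text and one small regression per organ and time point, on data acquired or implied already. The downside is imprecision: a slope half-width of about 0.23 to 0.70 against an expected size of 0.5, so the interval must always be shown. In addition, because activity is nearly constant within the arm, activity per kg and weight move together. A single slope will absorb both dilution and attenuation, and applying it to a weight-scaled design also needs a stated model. No change to dose or procedures is proposed.

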### *C. To collect preliminary data about total body FDG perfusion and early biodistribution .*

Population: Study Arms 1-3

Explanation: Total body EXPLORER PET images will be obtained for the first 60 minutes following injection. Organ perfusion and early FDG biodistribution will be evaluated with time-activity curves and mathematical analysis generated for different organs using regions of interest (ROIs).

### *D. To obtain preliminary data to understand whether intravenous iodinated contrast agent produce a significant change in quantification of FDG uptake levels.*

Population: Study Arm 3

Explanation: Regions of interest will be placed in several organs; pixel intensities within ROI will be recorded. Data reconstructed using contrast-

PROTOCOL TITLE: [1341792] EXPLORER PET/CT: A Pilot Evaluation in Healthy

Volunteers

Version 9 01/27/2021

enhanced CT for attenuation correction will be compared to data reconstructed using non-contrast enhanced CT for attenuation correction.

Participants will be asked to fast for 6 hours prior to arriving at the EXPLORER Molecular Imaging Center ([name]) on the day of their PET imaging study visit. A technologist will screen the participants to evaluate their readiness for PET scanning using the standard UC Davis Radiology approved form. A urine pregnancy test will be administered to all women of child-bearing potential, at no charge. Blood glucose level will be tested using the standard

PROTOCOL TITLE: [1341792] EXPLORER PET/CT: A Pilot Evaluation in Healthy

Volunteers

Version 9 01/27/2021

fingerstick method by standard operating procedures, at no charge. Following this, an intravenous (IV) line will be placed in the forearm by the study PET/CT technologist or study physician and the participant will be positioned supine on the scanner table. From the time of injection with FDG we will collect urine from all subjects until the scan visit at EXPLORER is complete. Subjects will be asked to urinate into a portable unisex urinal. After the total amount of excreted FDG is assessed and recorded, we will dispose of the urine sample. We will also ask all subjects if they had a bowel movement from the time they are injected with FDG until they complete their scan(s).

*Arm 1 (N=15; delayed imaging acquisition):*

For Study Arm 1, 10 +/- 2 mCi of F fluorodeoxyglucose (FDG) will be hand injected through the IV and a 60-minute dynamic scan will begin on EXPLORER. The IV line will be removed after dynamic acquisition. The dynamic scan will be preceded by ultra low-dose (estimated dose of 1.298 mSv) CT scan. This CT scan will provide information for attenuation correction for the PET data. At 90 minutes, 3-, 6-, 9- and 12-hours, a static whole-body scan for 20 minutes will be acquired on EXPLORER. Prior to the 90-minute scan a low-dose CT (estimated dose of 7.44 mSv) will be obtained both for anatomic localization and for attenuation correction purposes. Prior to each of the later time-points (3-, 6-, 9- and 12-hours), an ultra low-dose (estimated dose of 1.298 mSv) CT scan will be acquired. This scan will be for attenuation correction purposes only. Following the 12-hour scan, the participant's study visit will be completed. Participants will be monitored for adverse reactions related to prolonged fasting (e.g. hypoglycemia) between scanning sessions. In addition, low carbohydrate snacks will be available following the 3-hour scan.

*Arm 2 (N=15; low FDG dose imaging):*

For Study Arm 2, 0.5 +/- 0.1 mCi of F-FDG (1/20th of the standard dose) will be hand injected through the IV and a 60-minute dynamic scan will begin on EXPLORER. The dynamic scan will be preceded by an ultra-low-dose CT scan (estimated dose of 1.298 mSv) for attenuation correction. The standard 20-minute EXPLORER scan obtained at 90 minutes will be obtained after a low dose CT (estimated dose of 7.44 mSv) for attenuation and co-localization. The standard 20-

PROTOCOL TITLE: [1341792] EXPLORER PET/CT: A Pilot Evaluation in Healthy Volunteers  
Version 9 01/27/2021  
minute EXPLORER scan obtained at 3 hours will be preceded by an ultra-low-dose CT scan (estimated dose of 1.298 mSv) for attenuation correction only.

*Arm 3 (N=15; comparison PET images reconstructed using CT-based attenuation correction acquired with and without iodinated contrast enhancement):*

For Study Arm 3, 10 +/- 2 mCi of F-FDG will be hand injected through the IV and a 60-minute dynamic scan will begin on EXPLORER. Prior to the dynamic scan, an ultra-low-dose CT scan (estimated dose of 1.298 mSv) will be acquired for attenuation correction purposes only. At 90 mins, a low dose non contrast enhancement CT (estimated dose of 7.44 mSv) will be acquired vertex to toes. Iodinated contrast (150 cc of iodine Omnipaque 350) will then be intravenously injected (through the same IV placed to inject FDG) at 3 ml/sec while the patient remains still on the scanner and a second low-dose CT will be acquired. Finally, a 20-minute PET acquisition will be performed. The IV line will be removed after completion of the study.

